### CGI-C

The results of the CGI-C assessments are presented in a listing together with the categories based on the SAF.

*For the CGI-Change, the proportion [n(%)] of patients rated as improved, as well as those showing no change or worsening, at each time-point will be calculated. This analysis is performed on the FAS as described in section 8.1 and repeated for the subgroups Age (<10 years, ≥10 years) and Region (India; Europe, Australia, Tunisia; United States).*

The CGI-C scores are plotted over time within stacked bar charts on the FAS.

### CGI-S

The individual items of the CGI-S are listed including the CGI-S overall rating (CGI-S structured) for the SAF.

The CGI-S score is analysed as a categorical variable as described in section 8.1. The summary statistics are presented for the FAS and repeated for the subgroups Age (<10 years, ≥10 years) and Region (India; Europe, Australia, Tunisia; United States).

The CGI-S (structured) scores are plotted over time with stacked bar charts for the FAS.

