### 16.2.6 *Efficacy Analyses*

Descriptive statistics (n, mean, standard deviation [SD], median, minimum, and maximum) will be provided for all continuous efficacy measures for actual values and changes from baseline of Study IEDAT-03 at each time-point. For categorical variables, the number and percentage of patients in each category will be presented at each time-point.

The analysis of long-term efficacy of EDS-EP is an exploratory objective of this extension study, and will be based on the results for the "Modified" International Cooperative Ataxia Rating Scale (mICARS), and the Clinical Global Impression of severity and change (CGI-S/C). Descriptive statistics will be performed to determine the proportion of patients who improve, maintain their current state, or worsen after one year of treatment with EDS-EP in this open-label extension study, compared to their baseline status at entry into the IEDAT-03-2018 trial. The mean (SD) change from baseline at each time-point will be evaluated for the mICARS and the CGI-S. For the CGI-Change, the proportion [n(%)] of patients rated as improved, as well as those showing no change or worsening, at each time-point will be calculated.

Additional analyses will be performed to determine the change in each of the efficacy measures compared to the baseline of the IEDAT-02-2015 study, comparing patients who were treated with EDS-EP throughout the double-blind and open-label treatment periods vs. those who received placebo for varying periods in Study IEDAT-02-2015, before being switched to the active treatment. As a secondary objective, similar descriptive analyses will be performed to evaluate the long-term effects of EDS-EP on health-related Quality of Life (QoL), as assessed by the EQ-5D-5L scale.

The details of the statistical analyses will be presented in a separate Statistical Analysis Plan.

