### 3. Protocol

This study is being conducted under the sponsorship of EryDel. The clinical monitoring, data management, statistical analysis and medical writing are performed by PPD under contract and in collaboration with EryDel.

This Statistical Analysis Plan (SAP) provides a complete, expanded and detailed description of the statistical methods outlined in the protocol IEDAT-03-2018 (OLE-IEDAT) version 7.0 (dated 01-DEC-2020). Text that has been copied from the protocol is formatted in italics to indicate that it is identical to the protocol, which should ease the review and avoid unnecessary alterations to text approved in the protocol.

All TLFs (Tables, Listings and Figures) of the final analysis, for inclusion in the CSR (Clinical Study Report) are produced by PPD.

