### 3.6 Changes in the Conduct of Study or Planned Analysis compared to protocol

According to section 16.2.1 of the protocol the safety analysis set should be defined as follows:

*Safety Population (SP): All subjects who receive a dose of study medication and have at least one post-dose safety assessment will be included in the safety analyses.*

However, to be in line with general guidance like ICH E9 it was decided to include all patients who received any dose of study medication during this OLE-IEDAT study into the safety analysis set, regardless of the presence of post-dose safety assessments.

The schedule of events in Section 3.3 of this SAP is a copy from the protocol apart from one difference: To clarify that in this SAP also uses baseline from the ATTeST study the column “Baseline” has been renamed to “OLE-IEDAT Baseline”.

Section 16.2.6 of the protocol states: *Additional analyses will be performed to determine the change in each of the efficacy measures compared to the baseline of the IEDAT-02-2015 study, comparing patients who were treated with EDS-EP throughout the double-blind and open-label treatment periods vs. those who received placebo for varying periods in Study IEDAT-02-2015, before being switched to the active treatment.*

However, as described in Section 6.3 of this SAP this comparison will not be limited to efficacy or the protocol defined groups and all summaries in this study will display the 7 treatment groups from the ATTeST study. Subgroups for Age (<10 years, ≥ 10 years) and Region (India; Europe, Australia, Tunisia; United States) are also included.

Section 12.1.1 of the protocol outlines the ICARS assessment, including a description of the “Modified” ICARS (mICARS). As described in Section 3.4 of this SAP, the “Rescored” mICARS is also considered as an endpoint in the analysis.

A definition of continuous exposure is added to Section 7.1 to support future analysis.

Visit periods of 12 months is assessed to Section 7.1 and these are used in summary of Adverse Events described in Section 10.7.1. To investigate Adverse Events by the period in which they occur.

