#### **Clinical Global Impression CGI S (structured)**

*The CGI-S scale measures global severity of illness at a given point in time, and is usually rated on a 7-point, Likert-type scale ranging from 1 (normal, not ill at all) to 7 (among the most extremely ill patients). However, no version of the CGI-S exists which has been specifically adapted for use in AT patients; therefore, a 5-point version was developed that takes into account the severity of the following symptoms of AT: ataxia (walking), dysarthria, dysmetria, extrapyramidal symptoms (chorea, myoclonus, dystonia, and tremor), and eye movements. Ratings of none (0), mild (1), moderate (2), severe (3) and very severe (4) are selected based on the level of symptomatology. Two independent versions of the CGI-S scale were developed, a structured scale, based on the 5 disease-related anchors and an unstructured scale based on the clinical judgment of an experienced physician. Both the structured and unstructured versions were field-tested. The final structured CGI-S score is based on the severity of the symptoms in each domain, as indicated below:*

- *A rating of 0 (not ill/asymptomatic) can be made only if there are no symptoms, or a rating of mild on only one symptom domain;*
- *A rating of 1 (mild) can be made only if there are not more than 2 domains rated greater than mild;*
- *A rating of 2 (moderate) can be made only if there are not more than 2 domains rated greater than moderate;*
- *A rating of 3 (severe) can be made only if there are not more than 2 domains rated greater than severe;*

- *A rating of 4 (very severe) can be made only if there are at least 2 domains rated as severe and at least 2 rated as very severe.*

The final structured CGI-S score is captured on the “CGI-S” eCRF Form as “CGI-S overall rating”.

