### **EQ-5D-5L index - change from OLE-IEDAT baseline**

The EQ-5D-5L index - change from OLE-IEDAT baseline is calculated at each relevant FU visit as:

- EQ-5D-5L index - change from baseline = EQ-5D-5L index at FU  
- EQ-5D-5L index at OLE-IEDAT baseline.

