## 8. Analysis Methods

### 8.1 General Methods

For continuous variables, the mean, standard deviation (SD), minimum, median and maximum as well as 1st and 3rd quartile (Q1, Q3) are presented, together with the total number of observations and the number of non-missing values. Unless otherwise specified minimum and maximum values are reported to the same number of decimal places as the recorded measurements, mean, median, 1st and 3rd quartile are reported to one more decimal place and standard deviation one additional decimal place more than the mean.

For categorical variables, absolute and relative frequencies are reported. Relative frequencies are based on all observations and reported as a percentage to one decimal place. Unless otherwise specified percentages are based on the number of patients with data and are not calculated for missing categories.

Adverse events, medical histories and concomitant medications are reported on a patient basis, i.e. if a patient reported several events coded to the same coding term the patient is counted only once at the respective level of display. The percentages are calculated using the number of patients in the population Analysis Set as the denominator.

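### The SAP drops, without declaring it, two outputs planned in protocol 16.2.6: mean (SD) change in CGI-S, and the one-year proportions who improve, hold steady or worsen

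*SAP*

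**What the plan says.** Protocol 16.2.6 (Efficacy Analyses) plans three outputs that matter here:

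- **CGI-S change.** "The mean (SD) change from baseline at each time-point will be evaluated for the mICARS and the CGI-S". The synopsis repeats this sentence.
- **One-year classification.** It plans "the proportion of patients who improve, maintain their current state, or worsen after one year of treatment with EDS-EP", judged against status at entry into IEDAT-03-2018. No scale or cut-off is named, and the synopsis does not contain this item.
- **Change from the earlier trial's baseline.** SAP 3.6 itself quotes this sentence: "Additional analyses will be performed to determine the change in each of the efficacy measures compared to the baseline of the IEDAT-02-2015 study".

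The SAP says in section 3 that it "provides a complete, expanded and detailed description of the statistical methods outlined in the protocol". For CGI-S, section 7.4.7 defines only the recorded overall rating ("The final structured CGI-S score is captured on the" CGI-S form). Section 10.6.1 then says "The CGI-S score is analysed as a categorical variable as described in section 8.1". Section 8.1 defines a categorical summary as absolute and relative frequencies, and adds: "Unless otherwise specified percentages are based on the number of patients with data and are not calculated for missing categories". The outputs are Tables 14.2-5.1 to 5.6, a stacked bar chart and a listing.

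SAP 3.6 declares changes to the safety set, a renamed baseline column, the treatment groups and subgroups, the rescored mICARS, continuous exposure and 12-month adverse event periods. It is silent on both outputs.

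**The concern.** CGI-S frequencies at separate visits are unpaired. Each visit's percentages use whoever has data at that visit, and that group changes over time; SAP 7.4.1 records, for example, that the sponsor terminated the study at sites in India because of COVID-19. The distribution can therefore look better because more severe patients have left, without anyone improving. The planned change from baseline compares each patient with himself or herself. It avoids that artefact, although it still describes only the patients seen at the visit.

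The one-year classification answers a different question: how many patients held or lost ground. In a progressive disease that is a natural thing to report from a long-term extension, and the protocol planned to report it. Because the protocol left the scale and cut-offs open, the SAP was the place to define them.

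A reader who relies on the SAP's claim to completeness and on its list of changes would not learn that either output had been dropped.

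**Working it through.** **Step 1. Set the plan against the SAP.**

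| Protocol 16.2.6 output | SAP derivation (7.4.7) | SAP output (10.6.1, section 12) | Declared in 3.6? |
|---|---|---|---|
| mICARS mean (SD) change | Yes, both baselines | Yes | Not needed |
| CGI-S mean (SD) change from extension baseline | None | None | No |
| CGI-S change from ATTeST baseline | None | None | No |
| Improve / maintain / worsen at one year | None, any scale | No table, any scale | No |

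The SAP does derive change where it means to. It has change variables for mICARS, the rescored mICARS, full ICARS and EQ-5D-5L ("The EQ-5D-5L index - change from OLE-IEDAT baseline is calculated at each relevant FU visit as" the follow-up value minus the baseline value). EQ-5D-5L is a tertiary objective in the SAP, and its change is summarised from both baselines. CGI-S is part of the secondary objective, and its change is summarised from neither.

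The nearest output to the one-year classification is CGI-C. The protocol plans that in a separate sentence, and SAP 7.4.7 tabulates it in two groups: scores 1-3, and scores 4-7 pooled.

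**Step 2. What unpaired percentages can hide when patients leave.** All figures in Steps 2 and 3 are assumed. They are illustrations and bounds, not estimates. Score mild = 1, moderate = 2, severe = 3. Start with 100 patients at 20/50/30, so the mean is (20×1 + 50×2 + 30×3)/100 = 2.10.

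- *10 severe patients leave, nobody changes.* 20/50/20 of 90. Severe share 20/90 = 22.2%. Mean 180/90 = 2.000, a fall of 0.10. Paired change 0.
- *20 severe patients leave, nobody changes.* 20/50/10 of 80. Severe share 10/80 = 12.5%. Mean 150/80 = 1.875, a fall of 0.225. Paired change 0.
- *20 severe patients leave and 10 moderate patients become severe.* 20/40/20 of 80. Severe share 20/80 = 25.0%, down from 30%. Mean 160/80 = 2.000, a fall of 0.10. Paired: 10/80 = 12.5% worsened, none improved, mean change +10/80 = +0.125.

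In the third case the by-visit display moves in the opposite direction to the patients.

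**Step 3. What unpaired percentages can hide with no dropout.** Limit moves to one level. Let a be mild to moderate, b moderate to mild, c moderate to severe, d severe to moderate, all in percent of patients. Worsened = a + c and improved = b + d. The SD of change is √[(worsened + improved) − (worsened − improved)²], with both as proportions.

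- *20/50/30 at both visits.* The margins force a = b and c = d, with a ≤ 20, c ≤ 30 and b + c ≤ 50. Worsened ranges from 0 to 20 + 30 = 50%. SD 0 to √(0.50 + 0.50) = 1.00.
- *One third in each level at both visits.* The same equalities hold, with b + c ≤ 33.3. Worsened ranges from 0 to 33.3%. SD 0 to √(2/3) = 0.82.
- *20/50/30 moving to 15/45/40.* a = b + 5 and c = d + 10, so worsened = b + d + 15. The limit b + c ≤ 50 gives b + d ≤ 40. Worsened ranges from 15% to 55%. Mean change is +0.15 throughout. SD runs from √(0.15 − 0.0225) = 0.36 to √(0.95 − 0.0225) = 0.96.

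The same pair of published distributions therefore fits very different shares of worsening patients.

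**The case against.** The strongest case on the other side is that little is lost, and several parts of it stand.

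- **Categories suit the scale.** CGI-S is a five-level ordinal rating, and 16.2.6 itself plans counts and percentages for categorical variables. A categorical analysis is defensible. The same section nevertheless names CGI-S for a mean change, so replacing it is a departure to be declared.
- **Paired information survives elsewhere.** mICARS, which the SAP calls the most important secondary efficacy endpoint, keeps its paired change from both baselines. CGI-S ratings are listed per patient. This limits the harm, but a listing is not a pre-specified paired summary.
- **The one-year sentence is loose.** It names no scale, and the stacked bars of CGI-C scores can show improved, unchanged and worse patients separately at Month 12. Pooling score 4 with 5-7 in the CGI-C tables is allowed by the protocol's CGI-C wording and is not itself a departure. But CGI-C is planned separately, and the SAP gives its reference only as baseline, so it does not clearly supply the one-year classification.
- **The India example proves little.** The documents do not say those patients were more severe or left before Month 12. CGI-S is also tabulated by region, with India separate. That is correct: the example shows that the patients present change, not the direction of any bias.
- **The illustrations are partly beside the point.** The SAP prints no CGI-S mean, so a falling mean level would not appear; the severe share would. With no dropout, the mean change can be recovered from the two distributions, and only the SD and the proportions are lost. The upper bound of 50% needs every patient to move, half in each direction, which is implausible here.

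Table shells and the separate document listing the submission outputs were not available, so the finding concerns the SAP text and its table titles.

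**Conclusion.** The concern holds. The SAP as written specifies neither the CGI-S mean (SD) change nor the one-year improve, maintain or worsen proportions, and section 3.6 declares neither omission. CGI-S change from the ATTeST baseline is missing as well. This follows from the text alone and needs no numerical assumption.

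The size of any distortion cannot be estimated from the documents. The illustrations rest on an assumed 20/50/30 split, assumed selective loss of severe patients and moves of at most one level. They show that an unpaired display can reverse the apparent direction (severe share 30% to 25.0% while 12.5% worsen), and that unchanged margins can fit anything from 0 to 50% worsening.

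The consequence is moderate. Efficacy is descriptive, without hypothesis tests, and neither the primary safety objective nor any error rate is touched. It should be corrected because the correction is cheap and a planned paired analysis would otherwise disappear unannounced.

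**What to change.** 1. In SAP 7.4.7, derive CGI-S change from OLE-IEDAT baseline and from ATTeST baseline. In 10.6.1, report mean (SD) change at each visit with the paired n. A shift table is optional.
2. Report the Month 12 proportions with a decrease, no change or an increase in CGI-S level against OLE-IEDAT baseline.
3. State which other scales the one-year sentence covers. For mICARS, either pre-specify a cut-off with its reason or declare the classification not done; protocol 7.3 and 12.1.2 say no data define a clinically relevant ICARS change. Use CGI-C only if the SAP states that it is rated against entry into the extension, since CGI-C is also listed among the extension's baseline assessments taken at ATTeST Month 12.
4. Preferably, tabulate CGI-C as improved (1-3), no change (4) and worsened (5-7), so that the tables separate stable from declining patients.
5. Declare in SAP 3.6, with the reason, any part of protocol 16.2.6 that is still not done. This is the minimum.

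The cost is one derived variable with two baselines, extra rows in Tables 14.2-5.1 to 5.6, one Month 12 table, one CGI-C row and SAP wording. Datasets and tables are double programmed (SAP 5.3), so the programming is done twice. No new patient data are needed.

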### EQ-5D-5L

The individual items of the EQ-5D-5L are listed including the values of the VAS, as well as the EQ-5D-5L index and its change from baseline. The listing is presented for patients in the SAF.

The EQ-5D-5L index at baseline and each relevant follow-up visit (every 6 months), and the change from OLE-IEDAT baseline and from ATTeST baseline to each relevant follow-up visit are summarized using summary statistics appropriate for continuous data as described in section 8.1. These summary statistics on the change from ATTeST baseline to each relevant follow-up visit are repeated for the subgroups of placebo patients and non-placebo patients of the ATTeST study. These summary statistics are presented for the FAS.

For the FAS, the mean EQ-5D-5L index is plotted over time with a trend line.

#### 10.6.1.1 Confirmatory Analysis

Not applicable in this single arm study.

#### 10.6.1.2 Sensitivity Analysis

Not applicable in this single arm study.

## 10.7 Safety Results

### 10.7.1 Adverse Events

#### Brief Summary of Adverse Events

An overview of AEs (including the number of patients with at least one TEAE, at least one TESAE, at least one TEAE leading to Death, at least one AESI, the number of patients who permanently withdrew the Study Treatment due to a TEAE, AEs during COVID-19 interruption, the worst intensity of any TEAE experienced by each patient with at least one TEAE and the closest relationship to Study Treatment of any TEAE experienced by each patient with at least one TEAE) is summarized for the SAF.

This summary is repeated for each 12-month period as described in Section 7.1.

### Display of Adverse Events

Adverse events are summarized on a per-patient basis (i.e. if a patient reported the same event repeatedly the patient is counted only once at the specific level of display) and on a per event basis. Absolute counts (n) and percentages (%) are presented for the number of patients with at least one Adverse event, and per SOC and per PT within SOC, for the SAF. Percentages are based on the number of patients in the population.

Descriptive tables are ordered by descending frequency of the overall number of patients within each SOC, and then ordered within each SOC by the number of patients within each PT. In the event of equal frequencies, tables are ordered by number of events in the respective category and, in the event of a tie, alphabetically.

AEs are summarized for the SAF as follows:

- Treatment-Emergent Adverse Events
- Treatment-Related Treatment-Emergent Adverse Events
- Adverse Events of Special Interest
- Treatment-Emergent Adverse Events by worst intensity
- Treatment-Emergent Adverse Events leading to death
- Treatment-Emergent Serious Adverse Events
- Treatment-Emergent Adverse Events that led to discontinuation of Study Treatment.
- On dose Treatment-Emergent Adverse Events During COVID-19 Treatment Interruption.
- Off dose Treatment-Emergent Adverse Events During COVID-19 Treatment Interruption.
- Restart Treatment-Emergent Adverse Events After COVID-19 Treatment Interruption.

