#### **Adverse Events During COVID-19 treatment interruptions**

For patients with treatment interruptions that result in gaps in dosing of greater than 60 days, adverse events are only considered treatment emergent if they occur within 60 days following the last dose. Adverse events that occurred greater than 60 days following the last dose will not be considered treatment emergent. For this population of patients whose long treatment interruption was due to COVID-19, three types of summarizations will be prepared:

- On dose (treatment emergent) adverse events
- Off dose (not treatment emergent) adverse events. Off dose events are those that occur during a period >60 days following a dose and prior to the immediately following dose.
- Restart (TEAE after restart of treatment) adverse events. Restart events are those that occur on/after the first dose after an off-dose period and prior to the start of any following off dose period.

Times to be considered as treatment interruptions due to Covid-19 are provided by EryDel in form of an excel spreadsheet.

|   |         |  |
|---|---------|--|
| CD+4 Lymphocyte count   | x10E9/L | Month 6 and Month 12   |
| Early morning Plasma Cortisol testing for Adrenal Insufficiency | µg/dL   | As needed: when patients are symptomatic, and when patients are at most risk for adrenal insufficiency and adrenal crisis, such as following discontinuation or interruptions of dexamethasone dosing |
| High dose ACTH stimulation test                                 | µg/dL   | As needed: In the event that patients show signs or symptoms of adrenal insufficiency during the study  |

All laboratory assessments are performed at local laboratories. Quantitative laboratory results are converted to their respective Reporting units for use in summary tables. Assessment of results as being within the normal range are made by the local laboratory. *Any laboratory abnormalities meeting the definition of an adverse event should be recorded on the Adverse Events CRF.*

Clinically notable values of standard laboratory are derived based on SI units as outline in Appendix 13.1.

If repeat tests are performed at any visit the result documented under the nominal visit label is used in all summaries and analyses for that Visit.

Baseline is as described in Section 7.1.

The change from baseline is calculated for quantitative laboratory tests at each scheduled post-baseline visit as:

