### Adverse Events

|                    |   |     |   |
|--------------------|---|-----|---|
| Table 14.3.1-1.1.1 | Summary of Adverse Events   | SAF | U |
| Table 14.3.1-1.1.2 | Summary of Adverse Events by 12 Month Period  | SAF | U |
| Table 14.3.1-1.2   | Treatment Emergent Adverse Events by System Organ Class and Preferred Term  | SAF | U |
| Table 14.3.1-1.3   | Treatment Related Treatment Emergent Adverse Events by System Organ Class and Preferred Term                              | SAF | R |
| Table 14.3.1-1.4   | Adverse Events of Special Interest by System Organ Class and Preferred Term   | SAF | R |
| Table 14.3.1-1.5   | Treatment Emergent Adverse Events by Worst Intensity by System Organ Class and Preferred Term                             | SAF | R |
| Table 14.3.1-1.6   | Treatment Emergent Adverse Events Leading to Death by System Organ Class and Preferred Term                               | SAF | R |
| Table 14.3.1-1.7   | Treatment Emergent Serious Adverse Events by System Organ Class and Preferred Term  | SAF | R |
| Table 14.3.1-1.8   | Treatment Emergent Adverse Events That Led to Discontinuation of Study Treatment by System Organ Class and Preferred Term | SAF | R |
| Table 14.3.1-1.9   | On Dose Treatment Emergent Adverse Events During COVID-19 Treatment Interruption by System Organ Class and Preferred Term | SAF | R |
| Table 14.3.1-1.10  | Off Dose Adverse Events During COVID-19 Treatment Interruption by System Organ Class and Preferred Term                   | SAF | R |
| Table 14.3.1-1.11  | Restart Treatment Emergent Adverse Events After COVID-19 Treatment Interruption by System Organ Class and Preferred Term  | SAF | R |

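### The on-dose, off-dose and restart adverse event tables have no time at risk and a denominator that includes patients who never entered the phase, so equal event rates can look like a drug or withdrawal effect

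*SAP*

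**What the plan says.** SAP 7.4.8 (Adverse Events During COVID-19 treatment interruptions) covers patients whose gap in dosing exceeds 60 days. For them, "adverse events are only considered treatment emergent if they occur within 60 days following the last dose". It then defines the other two phases: "Off dose events are those that occur during a period >60 days following a dose and prior to the immediately following dose", and "Restart events are those that occur on/after the first dose after an off-dose period and prior to the start of any following off dose period". The section says the three summaries are for the patients whose long interruption was due to COVID-19. The gaps themselves are not in the SAP: "Times to be considered as treatment interruptions due to Covid-19 are provided by EryDel in form of an excel spreadsheet".

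SAP 10.7.1 and the table list in SAP 12.1 give each phase its own table by system organ class and preferred term in the Safety Analysis Set (Tables 14.3.1-1.9, 1.10 and 1.11; the second is titled "Off Dose Adverse Events During COVID-19 Treatment Interruption by System Organ Class and Preferred Term"). On the denominator, SAP 10.7.1 states "Percentages are based on the number of patients in the population", and SAP 8.1 states "The percentages are calculated using the number of patients in the population Analysis Set as the denominator". Events are summarised per patient "and on a per event basis". No adverse event table in the plan carries patient-years, phase duration or an exposure-adjusted rate.

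**The concern.** A percentage of patients with at least one event rises with the time over which events can occur. The three phases have no common length. On-dose time has a stated end but no stated start. Off-dose time is whatever remains of the gap after day 60. Restart time runs to the next off-dose period, if there is one, in a study with open-ended treatment. Three tables side by side labelled on, off and restart invite the reader to ask whether events stop off drug and return on restart. As planned, the answer would mix the event rate with phase length.

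The denominator adds a second distortion. A patient with no gap cannot have an off-dose or restart event, and a patient who never resumed cannot have a restart event, yet both count in the Safety Analysis Set. This also conflicts with SAP 7.4.8, which limits the summaries to interrupted patients.

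Safety is the primary objective, and SAP section 9 says analyses of this study will support a submission, so these tables are likely to be read closely.

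**Working it through.** The plan gives no figure to reproduce: no event rate, phase length or number of interrupted patients. The check asks what the planned tables would show if the drug had no effect on event rates.

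**Model.** One constant rate r in all phases. The expected proportion with at least one event in a phase of T years is 1 − exp(−rT); expected events per patient are rT.

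**Illustration (assumed: r = 1 first event per patient-year; 18, 4 and 9 months), among patients who enter each phase**
- On dose: 1 − exp(−1.5) = 78%
- Off dose: 1 − exp(−0.333) = 28%
- Restart: 1 − exp(−0.75) = 53%
- On/off ratio: 77.7/28.3 = 2.7, with no drug effect.

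**A rate taken from the documents.** Protocol 7.1.3.1 reports 29 treatment-emergent events in 22 patients over 6 months: 29/(22 × 0.5) = 2.64 per patient-year, assuming full follow-up. With the same phase lengths, on dose is 1 − exp(−2.64 × 1.5) = 98%, off dose 1 − exp(−2.64 × 0.333) = 58%, ratio 1.7.

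**Sensitivity to phase length (assumed lengths in days)**

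| On dose | Off dose | r = 0.30: on vs off (ratio) | r = 2.64: on vs off (ratio) |
|---|---|---|---|
| 425 | 30 | 29.5% vs 2.4% (12.1) | 95.3% vs 19.5% (4.9) |
| 425 | 120 | 29.5% vs 9.4% (3.1) | 95.3% vs 57.9% (1.6) |
| 425 | 305 | 29.5% vs 22.2% (1.33) | 95.3% vs 88.9% (1.07) |
| 60 | 305 | 4.8% vs 22.2% (0.22) | 35.1% vs 88.9% (0.4) |
| 240 | 240 | 17.9% vs 17.9% (1.0) | 82.3% vs 82.3% (1.0) |

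The fourth row takes on dose as only the 60 days after the last dose before the gap, a reading that the title of Table 14.3.1-1.9 permits because it places these events during the interruption. The apparent direction then reverses. The lower rate is closer to what a single preferred term might show; the higher rate is for any event.

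**Denominator.** Assume a Safety Analysis Set of 100, of whom 60 were interrupted and 45 restarted, with r = 0.30 and phases of 425, 120 and 365 days. The printed percentages would be 60/100 × 29.5% = 17.7%, 60/100 × 9.4% = 5.6% and 45/100 × 25.9% = 11.7%. A 5,000-run Poisson simulation gave the same percentages, and events per patient-year at risk of 0.30 in all three phases. The rate removes the artefact.

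**Does anything else in the SAP repair this?**
- Event counts are planned, but rT grows in proportion to time.
- Duration of treatment (SAP 7.4.6) runs from first to last infusion, includes the gap and is not split by phase.
- The 12-month split (SAP 7.1, 10.7.1) applies to the adverse event overview, not to these three tables.
- Continuous exposure (SAP 7.1) is held for possible future work.

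**Definitions set side by side.** An event shortly after a restart dose also lies within 60 days of a dose, so the on-dose and restart definitions can overlap. The list in SAP 10.7.1 labels off-dose events treatment-emergent; SAP 7.4.8 says in this passage that they are not; and the general definition in the same section counts every adverse event in this study as treatment-emergent.

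**The case against.** The plan makes no comparison between phases. These are three separate descriptive tables, safety methods are descriptive throughout, and no objective concerns stopping or restarting treatment. That stands: the contrast is one a reader would draw, and the documents do not support calling it central to the primary safety endpoint, which is the occurrence of treatment-emergent events, serious events and discontinuations, with changes in safety parameters. Nor are these tables shown to be the only evidence on interrupted dosing: SAP 6.3 also defines a subgroup with more than 76 days between the parent trial and this one.

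A reader might infer that the tables will show a false effect, or that they report percentages alone. Neither follows. Gap dates and the number of interrupted patients are not in the documents, every phase length above is assumed, and the artefact is absent with equal lengths and small when percentages approach 100%. Event counts are already planned, though they do not solve the problem.

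The population point could be called a wording conflict, since SAP 7.4.8 already has the narrower group. That is fair, but SAP 8.1, 10.7.1 and the table list all point to the Safety Analysis Set, and a programmer working from them would use it. Table shells and the separate list of submission outputs are not available, so they may settle some of this.

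Finally, rates would not make the phases fully comparable. They run in fixed time order, off-dose time coincides with the pandemic, and events may be picked up less completely without monthly infusion visits. This argues against insisting on within-patient rate ratios, not against showing time at risk.

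**Conclusion.** The concern holds as a matter of presentation and definition. As written, the three tables can show different percentages in on-dose, off-dose and restart phases when the event rate is identical, and can suggest either a drug effect or a withdrawal effect. Under the assumed values the on/off ratio ranges from 12.1 to 0.22; it is 1.7 with the pilot-study rate and phases of 18 and 4 months, and 1.0 with equal lengths. None of these sizes can be confirmed without the sponsor's interruption dates, a stated start for the on-dose phase and the number of interrupted patients. Two parts need no assumption: the tables have no time at risk, and the Safety Analysis Set denominator conflicts with the restriction in SAP 7.4.8. The change should be made before the tables are produced, and the analysis should stay descriptive.

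**What to change.** 1. In SAP 7.4.8, state the start and end of each phase so that the phases are mutually exclusive, using infusion dates together with the sponsor's COVID-19 interruption dates. Say where off-dose time ends for a patient who never resumes.
2. Base each of Tables 14.3.1-1.9 to 1.11 on the patients who enter that phase, and align SAP 10.7.1 and 12.1 with SAP 7.4.8.
3. Beside n (%) and event counts, print patient-years at risk and events per 100 patient-years with 95% confidence intervals, using an interval method that allows for repeated events in one patient.
4. Reconcile the treatment-emergent label on off-dose events in SAP 10.7.1 with SAP 7.4.8, including its general definition of treatment-emergent events.
5. Add a footnote that phases run in fixed time order, that off-dose time coincides with the pandemic, and that ascertainment may differ without monthly infusion visits. Within-patient rate ratios are optional.

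The cost is SAP wording and programming. Infusion dates, event dates and the interruption spreadsheet are already part of the planned data, so no new collection is needed.
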